Proton Magnetic Resonance Spectroscopy (¹H-MRS) for Glutamate and GABA: This will occur prior to randomization (see above) and again at week 3 (window between days 17-24) of study medication between 2-4 hours after the last gabapentin/placebo dose to standardize acute dosing effects. Subjects will be breathalyzed prior to the scan and need to be zero (or will be rescheduled ASAP), and, if smokers, the time of last cigarette will be recorded. In an ongoing trial we have found no problems with imaging (fMRI) clinical trial participants twice (baseline/week 3) – very few have to be rescheduled due to drinking and some subjects find it intriguing. Each scan takes about 60 minutes and uses the following protocol: A structural scan will be taken for ¹H-MRS voxel placement and tissue segmentation (256 sagittal slices; 1mm thick/50% gap). The ACC voxel for ¹H-MRS will be placed on midsagittal T1-weighted images, anterior to the genu of the corpus callosum, with the ventral edge of the voxel aligned with the dorsal edge of the genu and a voxel size of 3 x 2.5 x 2.5 cm³ will be selected (consistent with Umhau, 2010 and Mon, 2012). Following auto-shimming, single-voxel water-suppressed ¹H-MRS spectra will be acquired using a Point Resolved Spectroscopy (PRESS) sequence: Repetition Time (TR) = 2000ms; Echo Time (TE) = 40ms; number of averages = 256); an unsuppressed water spectrum will be co-acquired (TE = 40ms, number of averages = 16), scaled for partial volume effects and relaxation, and used as a concentration reference. This sequence has been shown to

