Lab and Genetic Assays: The CNL lab directed by [name] has 20 years of experience in measuring carbohydrate deficient transferrin (CDT) and currently runs a state-of-the-art HPLC based assay that is recognized by the IFCC as a candidate reference method (Helander, 2010). The analyte of interest is disialo-CDT as a percentage of total transferrin (%dCDT). Extensive quality control and proficiency testing is routinely performed. His lab also assays urinary Ethylglucuronide (EtG), a sensitive measure of any/low alcohol consumption using a Microgenics immunoassay which correlates highly with LC-MS. Qiagen DNA extraction kits are used to extract DNA from whole blood by a dedicated genetic technician in his lab, tested for DNA purity, and used in Taqman PCR analysis with specific probes and primers purchased from Life Science Technologies using a Step One analyzer (Applied Biosystems). His K05 funding allowed him to become proficient in this type of analysis (Anton, 2012) and he has genotyped hundreds of samples with various SNP's and VNTR's including the glutamate and GABA genes of interest (see background section).

Outcome Variables and Power Analyses: The primary drinking outcome variable will be the percent of subjects with no heavy drinking days (PSNHDD) as defined by Falk (2010), chosen because it is currently accepted by the FDA in its guidance for clinical trials and also is consistent with our prior work with gabapentin. However, other secondary drinking variables such as percent days abstinent, % heavy drinking days, and drinks per day, as well as craving (OCDS) and biomarkers (%dCDT and GGT) will be calculated and reported for completeness sake. Urinary riboflavin and pill counts will be used as measures of compliance and compared between groups while potentially serving to define compliers for independent analysis. PSQ, POMS, and MES will evaluate sleep quality, mood state, and medication effect differences between medication groups. Pre-randomization and week-3 brain glutamate and GABA levels will be calculated for each subject and their change will be the unit of measurement for the treatment effect mediator analysis (see below).

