A statistical power calculation was conducted using data from our past two studies (background section) using the treatment effect in subjects with a DSM-IV history of AW on the PSNHDD outcome variable. With 45 subjects per medication group (total N=90) the power to detect the gabapentin treatment effect on PSHDD is between .83 (study 1 calculation) and .98 (study 2 calculation). While significant covariate effects in our earlier studies have not been observed with this outcome variable, additional power analysis using Monte Carlo simulation (n=500) in the presence of covariates modeled, (e.g. pretrial drinking, OCDS, ADS, etc.) on our previous studies was conducted. Power values comparable to those in the simpler analysis were found in all cases ranging from .81 to .87 (study 1) to .95 to .99 (study 2).

The statistical power calculation for gabapentin's effect on brain glutamate change from baseline to week-3 is based on the work of Umhau (2010), the study design closest to our own, where an acamprosate-induced change in brain glutamate levels (vs. placebo) was detected with an effect size of .95. *The power to detect a similar gabapentin vs. placebo difference in the current proposal with an n=45/group is in excess of .99 with the ability to detect an effect size as low as $d = .6$ with power of .8. Since the reported effect of gabapentin on GABA is quite large (Cai, 2012; Kuzniecky, 2002; Petroff, 1996; Petroff, 2000) the power to detect a gabapentin vs. placebo difference with an n=45/group is in excess of .9. Given this large statistical power, an expected maximal 10% attrition due to inadequate scans should not materially affect our ability to detect a medication effect on glutamate or GABA. Additionally, there is likely to be sufficient variation in both medication response and brain glutamate/GABA level change to allow acceptable use of a mediation analysis to examine the effect of this glutamate/GABA change on treatment response.*

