Power has not been calculated for the exploratory genetic analyses. The genetic SNP's we have chosen to explore are not only indicated by the literature but also, importantly, have a reasonable genotypic distribution. Given our past work and HapMap data (see Preliminary Data section) we expect the distribution of both the *GABRA2* and *GM8* allele frequencies to be about 60:40 with not much difference between Euro-Caucasians and African Americans. This should provide a good balance between treatment groups. Modifier effects are likely to be observable if the effect size is moderate to large. In any case, this data will allow more appropriate power calculations for subsequent studies. Effects of genetic variation on brain glutamate/GABA are unknown and completely novel but as a main effect with 90 subjects (even accounting for drop-outs or unusable scans) the power to detect a gene by analyte effect should be sufficient if clinically meaningful.

Data Analysis Plan: *The PSNHDD (with baseline percent heavy drinking days as a covariate) will be analyzed with a multiple logistic regression with indicator coding medication group as the primary independent variable. All hypotheses (primary, secondary) will be assessed with likelihood ratios. Other possible pre-randomization variables, e.g. sex, smoking status, ADS score, pre-randomization CIWA-Ar score, etc. will be evaluated as possible covariates in the final analysis. Missing data (assuming monotonicity) will be imputed as heavy drinking days. In addition, the relapse time-course will be analyzed by GEE techniques for the full treatment X time factorial design. Secondary outcome variables, e.g. other drinking variables, OCDS, POMS, PSQ index, MES and biomarkers (%dCDT and GGT), will be analyzed as either mixed models (SAS PROC MIXED) or in GEE analyses (SAS GENMOD) depending upon the nature of the variable (parametric or categorical).*

Change in glutamate and GABA levels will be analyzed as a mixed model (SAS PROC MIXED) with time as a within subject variable and medication group as between subject variables. Significant interactions will be interpreted with simple effects and main effects will be assessed in the absence of the interaction. If sex and smoking status (reported by some to effect brain GABA levels), or pre-randomization CIWA-Ar score are found to significantly influence glutamate or GABA levels, or if their inclusion reduces residual variance, they will be included in the model as covariates.

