
In order to assess the degree to which changes in brain GABA and glutamate account for drinking outcomes, neurochemical variables (as difference scores) will be entered into the main logistic regression model. A reduction in the significance of the main treatment effect or the treatment by time interaction will be suggestive of a mediation effect. Path analysis will be used to test the significance of the indirect path from treatment to GABA/glutamate levels to relapse status and/or other drinking measures.

Timeline: Since our staff is trained in all procedures and scales are digitalized, the first 3-4 months will be used for medication production, database building, and data collection computer tablet study specific program production. In the first year we will screen/randomize 38/18 subjects and then 57/27 subjects in year 2-3 and 38/18 subjects in year 4. The last five months will be used for data analysis and publication production.

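### A fall in the significance of the treatment effect does not show mediation, and the outcome window for the mediation analysis is not stated

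*Combined protocol and SAP*

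**What the plan says.** Under Data Analysis Plan, the mediation step says that "neurochemical variables (as difference scores) will be entered into the main logistic regression model". It then gives the reading rule: "A reduction in the significance of the main treatment effect or the treatment by time interaction will be suggestive of a mediation effect". The next sentence adds a formal test: "Path analysis will be used to test the significance of the indirect path from treatment to GABA/glutamate levels to relapse status", or other drinking measures.

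The mediator is defined under Outcome Variables and Power Analyses from the pre-randomization and week-3 levels: "their change will be the unit of measurement for the treatment effect mediator analysis". The section on proton magnetic resonance spectroscopy places the second scan "again at week 3 (window between days 17-24) of study medication". The same power section allows for "an expected maximal 10% attrition due to inadequate scans".

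For the outcome, the plan states: "The primary drinking outcome variable will be the percent of subjects with no heavy drinking days (PSNHDD) as defined by" a cited source. General Design of the Study assesses outcome over 16 weeks of treatment. The main logistic model has one binary outcome per subject and so no time term. The treatment-by-time term in the rule must therefore come from the separate analysis in which "the relapse time-course will be analyzed by GEE techniques for the full treatment X time factorial design".

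**The concern.** The rule takes a weaker p-value as a sign of mechanism. A p-value also weakens when the standard error grows or subjects drop out, and neither has anything to do with mediation. The plan expects gabapentin to move the analyte, so adding the analyte should inflate the standard error of treatment. The better the drug hits its neurochemical target, the more often the rule points to mediation, even if the target is irrelevant to drinking.

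The second issue is time order. A mediator measured at days 17 to 24 cannot explain heavy drinking that came before it. If such drinking counts toward the outcome and also shifts the week-3 level, the indirect path can be significant with the causation reversed.

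The mechanistic aim is at stake: the Significance section would draw inferences about other medications from it.

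**Working it through.** **Inputs from the documents.** 45 per group; effect on glutamate d = .95, smallest detectable d = .6; up to 10% scan loss; stated power for the primary outcome .83 to .98; odds ratios 3.2 (study 1) and 4.4 (study 2); scan at days 17 to 24; dosing through day 112.

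**Assumed.** Two-sided 5% level; placebo rate of no heavy drinking .25 (range .15 to .35).

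**1. The plan's own power for the analyte.** Power is approximately Φ(d√(n/2) − 1.96).
- d = .95: .95 × √22.5 = 4.506, power .995 (plan: above .99).
- d = .6: .6 × √22.5 = 2.846, power .812 (plan: .8).

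Both figures reproduce.

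**2. Collinearity.** With 1:1 allocation, R² between treatment and score is d²/(d² + 4), and VIF = 1/(1 − R²).
- d = .95: .9025/4.9025 = .184; VIF = 1.23; standard error × 1.107.
- d = .6: .36/4.36 = .083; VIF = 1.09; standard error × 1.044.

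Stated power of .83 corresponds to an expected z of 2.914. Dividing by 1.107 gives 2.632, so power becomes .75. With 10% scan loss as well, 2.914 × √.9/1.107 = 2.497, and power is .70. No mediation is involved in either fall.

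**3. Simulation with an inert analyte** (logistic model, likelihood-ratio tests, 4,000 trials per cell, placebo rate .25, odds ratio 3.2):

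| d | p-value rises, same subjects | significance lost, same subjects | significance lost, 9 of 90 missing from the mediator model only |
|---|---|---|---|
| 0 | 50% | 1% | 8% |
| .6 | 64% | 7% | 16% |
| .95 | 71% | 15% | 22% |

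Losses are percentages of trials that were significant before the score was added. Repeat runs agree within about 3 percentage points. Over placebo rates .15 to .35, the same-subject losses are 1–2%, 6–10% and 13–20%. With odds ratio 4.4, the p-value rises in 67% (d = .6) and 77% (d = .95), and significance is lost in 4% and 7%. At odds ratio 3.2 and d = .95, the median log odds ratio for treatment was 1.19 before and 1.21 after. The estimate does not shrink; only its precision falls.

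**4. The treatment-by-time term.** GEE simulation with four time points and one change score per subject as a main term: p rises in 49–51% of trials at every d, no significance is lost, and the standard error ratio is 1.004–1.005. If 9 of 90 subjects are missing from the mediator model, 9–13% lose significance.

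**5. Time order.** Before the scan lie 17 − 1 = 16 to 24 − 1 = 23 of 112 days, or 14% to 21%. The indirect path was called significant when the treatment-to-analyte and analyte-to-outcome tests both had p < .05. The analyte had no effect on drinking, and the outcome covered the whole period. The shift caused by pre-scan heavy drinking and the share of relapses before the scan are assumptions:

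| Shift (SD) | False positives, 30–70% of relapses before scan |
|---|---|
| 0 | 4–6% |
| 0.25 | 4–12% |
| 0.5 | 10–34% |
| 1.0 | 21–82% |

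If only 10% of relapses precede the scan, the rate is 4–7%. Counting only post-scan drinking and adjusting for pre-scan heavy drinking also gives 4–7%. The post-scan window without adjustment, at 0.5 SD, gives 8–24% if 90% of pre-scan heavy drinkers drink heavily again, and 5–6% if 50% do. In a different model, where the drug moves the analyte only through early drinking, the whole-period rate is 3% (0.6 SD) and 11% (0.95 SD), against 1% with a post-scan outcome.

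**The case against.** The plan calls the fall in significance only suggestive and follows it at once with a path analysis. Collinearity does not bias that test: its false-positive rate is 4–6% when drinking does not shift the analyte, so an inert analyte that meets the rule would usually fail the formal test. This stands, and it limits the consequence. It does not rescue the rule, which remains a stated criterion.

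On time order, the size rests on assumptions. The outcome definition sits in a cited source that may contain a grace period, and the path-analysis outcome may be another drinking measure. The plan also reports that few scans in an ongoing two-scan trial were rescheduled for drinking. All of this stands. What keeps the point alive is the plan's own text. The preliminary data section says that timing relative to drinking and abstinence may influence these measurements. The first scan is confined to 3 to 7 days of sobriety partly because of GABA/glutamate levels. For the week-3 scan the only stated sobriety check is a zero breathalyzer.

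A reader might also infer that baseline confounding is ignored. It is not: baseline percent heavy drinking days is already in the main logistic model, and ADS score and smoking status are candidates. Simulating an unmeasured common cause (assumed .7 log-odds per SD on drinking; correlation .2, .3 or .5 with the analyte), false positives were 7–9%, 10–13% and 23–31% with no baseline covariate. A baseline proxy correlated .8 with the cause, in the whole-period outcome model, brought them to 5%, 5–7% and 8–10%. A proxy correlated .4 gave 8%, 10–11% and 19–23%. The existing covariate may therefore help, by an amount that depends on how good a proxy it is.

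**Conclusion.** The reading rule is wrong as written. For the main treatment effect, with an inert analyte, the p-value rises in about 64–71% of trials against a floor of 50%, and a significant effect is lost in about 7–15%. These figures rest on odds ratio 3.2, an assumed placebo rate of .25 and the plan's d of .6 to .95. Matters are worse if the models with and without the mediator use different subjects, which the documents leave open. For example, anyone who leaves before week 3 can be scored a heavy drinker by imputation yet has no change score.

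The missing outcome window is a secondary, conditional weakness. It matters only if pre-scan heavy drinking counts and alters the week-3 level. The risk is near nominal if few relapses precede the scan.

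Four stronger readings are not supported:
- That collinearity also distorts the treatment-by-time term. A single change score entered as a main term leaves that standard error essentially unchanged. For that term, only the general objection to p-value changes and the sample question apply.
- That no test of the indirect effect is planned. One is.
- That the path analysis is known to be biased by reverse causation. The documents give neither the shift nor the share of early relapses.
- That primary efficacy is compromised. It is not touched.

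**What to change.** Delete the sentence on reduced significance. Then:
- Base any mediation statement on the indirect effect already planned, reported with a confidence interval.
- Fit all mediation models, with and without the analyte, in one common sample of subjects with both usable scans.
- Keep baseline percent heavy drinking days in the mediation outcome model and use the same baseline covariates in the treatment-to-analyte path.
- State the outcome window for mediation, including any grace period in the cited definition.
- Add a sensitivity analysis, from the daily drinking data already collected, that counts heavy drinking only after the week-3 scan and adjusts for heavy drinking between randomization and the scan. As step 5 shows, restricting the window without that adjustment may not be enough.
- State that the indirect effect assumes no unmeasured common cause of analyte change and drinking. If the whole-period and post-scan results disagree, claim mediation only as exploratory.

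The cost is plan wording and a little more analysis, with no new data. The post-scan analysis is a sensitivity analysis because it trades power for time order and conditions on a post-randomization variable. With an assumed true mediator effect (odds ratio 2 per SD) and 30%, 50% or 70% of relapses before the scan, power of the indirect test falls from 81% to 71%, 60% or 44% at d = .95. At d = .6 it falls from about 67% to 56%, 47% or 32%. It does not remove confounding by an unmeasured common cause.
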